2.1 Hypothesis

We hypothesize that, for multiple myeloma (MM) patients with relapsed or refractory disease after anti-BCMA CAR-T therapies, pembrolizumab will be associated with a 30% or greater disease response rate (PR or greater).

2.2 Primary Objective and Endpoint(s)

Primary Objective	Endpoint(s)	Time Frame
To evaluate the overall response rate (ORR) of pembrolizumab in patients with relapsed or refractory MM (RRMM) after anti-BCMA CAR-T therapies	
 ORR (defined as the proportion of patients achieving a partial response (PR) or better based on IMWG criteria after 4 cycles of pembrolizumab therapy) 	From initiation of study treatment until after 4 cycles of therapy

2.3 Secondary Objective(s) and Endpoint(s)

Secondary Objective	Endpoint(s)	Time Frame
1. To evaluate the safety and tolerability of pembrolizumab in participants who relapsed or were refractory to anti-BCMA CAR-T therapies.	
 Frequency of adverse events, as graded by NCI CTCAE version 5.0, including frequency of non-hematologic grade 3 or higher adverse events Frequency of CRS graded by ASTCT Frequency of ICANS graded by ASTCT Frequency of treatment discontinuations due to toxicity 	From initiation of study treatment until safety follow-up following treatment discontinuation
2. To evaluate the depth of response for patients treated with pembrolizumab who had previously relapsed after or were refractory to anti-BCMA CAR-T therapies	
 Rates of sCR, CR, VGPR, PR, SD, and PD at any time during pembrolizumab therapy 	From initiation of study treatment until discontinuation of treatment
3. To evaluate time-to-event outcomes, including time-to-next treatment (TNT), progression-free survival (PFS), and overall survival (OS) after initiation of pembrolizumab therapy	
 TNT, PFS, OS assessed using Kaplan-Meier survival analysis 	From initiation of study treatment until end of follow-up

2.4 Exploratory Objective and Endpoint

Exploratory Objective	Endpoint(s)	Time Frame
To explore the immune profile after pembrolizumab treatment, including changes in absolute lymphocyte count (ALC) and lymphocyte subsets by flow-cytometry	
 ALC, absolute CD3 T-cell count, absolute CD4 T-cell count, and absolute CD8 T-cell count 	From initiation of study treatment until after 4 cycles of therapy

3 Study Design

3.1 Characteristics

This is a Phase II, single-center study of pembrolizumab for the treatment of relapsed or refractory multiple myeloma (RRMM) after anti-BCMA chimeric antigen receptor T-cell (CAR-T) therapy. Eligible patients will receive pembrolizumab 200 mg over 30 minutes, intravenously, every 3 weeks for up to 2 years (35 cycles) or until disease progression/dose-limiting toxicities/discontinuation. The study will utilize a Simon's two-stage design with 15 participants enrolled in stage I and 10 additional participants enrolled in stage II assuming that at least 2 or more participants achieve a treatment response after 4 cycles of therapy during stage I of the study. The primary endpoint will be overall response rate (partial response [PR] or better by International Myeloma Working Group [IMWG] criteria) after 4 cycles of therapy. A Bayesian toxicity monitoring design will be incorporated for ongoing safety analysis during the trial to pause enrollment if at any time the rate of grade 3 or higher non-hematologic adverse events exceeds 30%.

[figure not shown]

Figure 1 Trial Schema

3.2 Sample Size

Participants with relapsed or refractory MM after anti-BCMA CAR-T therapies will be included in this study. We anticipate enrolling 25 - 27 participants to allow for the possibility of 10%

participant dropout before receiving pembrolizumab therapy or during the response evaluation period.

- Stage 1: 15 participants will be accrued. The trial will be terminated at Stage 1 if 0 or 1 response is observed; otherwise, it will continue to Stage 2.
- Stage 2: 10 more patients will be accrued (for a total of 25 patients). We will reject the null hypothesis if 6 or more responses are observed in 25 patients.

If a participant is enrolled but does not receive any doses of pembrolizumab, the participant may be replaced.

If a participant is enrolled and receives less than 4 cycles of therapy and discontinues therapy or withdraws from the study for reasons other than disease progression, the participant will not be evaluated for the primary efficacy endpoint and will be replaced. However, all participants who receive at least one dose of pembrolizumab will be included in the safety analysis for adverse events (including those that received < 4 cycles of therapy).

3.3 Eligibility Criteria

3.3.1 Inclusion Criteria

In order to be eligible to participate in this study, an individual must meet all of the following criteria:

1. Male/female participants who are 18 years of age or older on the day of signing informed consent with histologically confirmed diagnosis of multiple myeloma will be enrolled in this study.
2. Ability to understand a written informed consent document, and the willingness to sign it or a legally acceptable representative (if applicable).
3. Have an Eastern Cooperative Oncology Group (ECOG) performance status <2 (Karnofsky >60%, see Appendix 1). Evaluation of ECOG is to be performed within 7 days prior to the start of study treatment.
4. The effects of pembrolizumab on the developing human fetus are unknown. For this reason, women of child-bearing potential and men must agree to use adequate contraception detailed in Appendix 3 for the duration of study participation and 120 days after last administration of study treatment.

(See Appendix 3 for more details) Female participants are eligible if not pregnant, not breastfeeding, and one of the following:

- a) Not a WOCBP as defined in Appendix 3

OR

- b) WOCBP who agrees to follow contraceptive guidance in Appendix 3 during treatment period and at least 120 days following last dose of study treatment

Should a woman become pregnant or suspect she is pregnant while she or her partner is participating in this study, she should inform her treating physician immediately.

Men treated or enrolled on this protocol must also agree to use adequate contraception prior to the study, for the duration of study participation, and 120 days after last

administration of study treatment. Men should also refrain from donating sperm during this period.

5. Participants must have either

- a. progressive disease after prior anti-BCMA CAR-T therapy and have not started another systemic anti-cancer therapy following progression after anti-BCMA CAR-T therapy. Patients who received localized radiotherapy alone for symptomatic relief of progressive disease following anti-BCMA CAR-T will be allowed.

OR

- b. stable disease as best hematologic response after at least 30 days post anti-BCMA CAR-T infusion.

Progression after anti-BCMA CAR-T is defined by International Myeloma Working Group (IMWG) criteria:

- a) Increase of > 25% from lowest response value in any one or more of the following:
 - i. Serum M-component and/or (the absolute increase must be > 0.5 g/dL)
 - ii. Urine M-component and/or (the absolute increase must be > 200 mg/24 h)
 - iii. Only in patients without measurable serum and urine M-protein levels; the difference between involved and uninvolved FLC levels. The absolute increase must be > 10 mg/dL
 - iv. Bone marrow plasma cell percentage: the absolute percentage must be > 10%

and/or:

- b) Definite development of new bone lesions or soft tissue plasmacytomas or definite increase in the size of existing bone lesions or soft tissue plasmacytomas

and/or:

- c) Development of hypercalcemia (corrected serum calcium > 11.5 mg/dL or 2.65 mmol/L) that can be attributed solely to the plasma cell proliferative disorder

Stable disease is defined by IMWG criteria: Not meeting criteria for sCR, CR, VGPR, PR, or PD (see Appendix 6)

6. Time from date of anti-BCMA CAR-T infusion to date of first administration of pembrolizumab (study drug) must be \geq 30 days. In order to be eligible for this study, participants must not be candidates for treatment regimens known to provide clinical benefit in MM as assessed by the treating physician and must have previously received

or are intolerant to a proteasome inhibitor, an immunomodulatory agent, and an anti-CD38 antibody.

7. Diagnosis of symptomatic multiple myeloma defined as: clonal bone marrow plasma cells >10% or biopsy-proven bony or extramedullary plasmacytoma and any one or more of the following CRAB features and myeloma-defining events:
 - a) Hypercalcemia: serum calcium >0.25 mmol/L (>1mg/dL) higher than the upper limit of normal or >2.75 mmol/L (>11mg/dL)
 - b) Renal insufficiency: creatinine clearance <40 mL per minute or serum creatinine >177 micromol/L (>2mg/dL)
 - c) Anemia: hemoglobin value of >20g/L below the lowest limit of normal, or a hemoglobin value <100g/L
 - d) Bone lesions: one or more osteolytic lesions on skeletal radiography, CT, or PET/CT. If bone marrow has <10% clonal plasma cells, more than one bone lesion is required to distinguish from solitary plasmacytoma with minimal marrow involvement
 - e) Any one or more of the following biomarkers of malignancy:
 - i. 60% or greater clonal plasma cells on bone marrow examination
 - ii. Serum involved / unininvolved free light chain ratio of 100 or greater, provided the absolute level of the involved light chain is at least 100 mg/L
 - iii. More than one focal lesion on MRI that is at least 5mm or greater in size
8. Active and measurable disease, defined by serum paraprotein (M-protein) ≥ 0.5 g/dL, 24-hour urine Bence Jones protein of ≥ 200 mg, or abnormal serum free light chain ratio with involved light chain of ≥ 10 mg/dL (100 mg/L).
9. Have adequate organ function as defined in the following table (Table 3.3.1). Specimens must be collected within 10 days prior to the start of study treatment.

Table 3.3.1 Adequate Organ Function Laboratory Values

System	Laboratory Value
Hematological	
Absolute neutrophil count (ANC)	$\geq 500/\mu\text{L}$ ^{a, b}
Platelets	$\geq 25\,000/\mu\text{L}$ ^{a, b}
Hemoglobin	$\geq 8.0\text{ g/dL}$ ^{a, b}
Renal	
Creatinine OR Measured or calculated ^c creatinine clearance (GFR can also be used in place of creatinine or CrCl)	$\leq 1.5 \times \text{ULN}$ OR $\geq 30\text{ mL/min}$ for participant with creatinine levels $>1.5 \times$ institutional ULN
Hepatic	
Total bilirubin	$\leq 1.5 \times \text{ULN}$ OR direct bilirubin $\leq \text{ULN}$ for participants with total bilirubin levels $>1.5 \times \text{ULN}$

AST (SGOT) and ALT (SGPT)	$\leq 2.5 \times \text{ULN}$ ($\leq 5 \times \text{ULN}$ for participants with liver metastases)
ALT (SGPT)=alanine aminotransferase (serum glutamic pyruvic transaminase); AST (SGOT)=aspartate aminotransferase (serum glutamic oxaloacetic transaminase); GFR=glomerular filtration rate; ULN=upper limit of normal.	
a Growth factor and/or transfusion support is permissible to stabilize participant prior to study treatment if needed.	
b No lower limit if cytopenia is related to bone marrow involvement.	

^c Creatinine clearance (CrCl) should be calculated per institutional standard.

Note: This table includes eligibility-defining laboratory value requirements for treatment; laboratory value requirements should be adapted according to local regulations and guidelines for the administration of specific chemotherapies.

3.3.2 Exclusion Criteria

An individual who meets any of the following criteria will be excluded from participation in this study:

1. A WOCBP who has a positive urine pregnancy test within 72 hours prior to study treatment initiation (see Appendix 3). If the urine test is positive or cannot be confirmed as negative, a serum pregnancy test will be required.

Note: in the event that 72 hours have elapsed between the screening pregnancy test and the first dose of study treatment, another pregnancy test (urine or serum) must be performed and must be negative in order for subject to start receiving study medication.

2. Has received prior therapy with an anti-PD-1, anti-PD-L1, or anti PD L2 agent or with an agent directed to another stimulatory or co-inhibitory T-cell receptor (e.g., CTLA-4, OX 40, CD137).
3. Has received prior systemic anti-cancer therapy including investigational agents within 4 weeks prior to study treatment initiation.

Note: Participants must have recovered from all AEs due to previous therapies to \leq Grade 1 or baseline. Participants with \leq Grade 2 neuropathy may be eligible.

Note: If participant received major surgery, they must have recovered adequately from the toxicity and/or complications from the intervention prior to starting study treatment.

4. Has received anti-BCMA CAR-T infusion < 30 days prior to study treatment initiation.
5. Has received subsequent systemic anti-cancer therapy following anti-BCMA CAR-T therapy. Participants who received localized radiotherapy alone for symptom control following anti-BCMA CAR-T therapy will be allowed to participate.
6. Has received a live vaccine within 30 days prior to the first dose of study drug. Examples of live vaccines include, but are not limited to, the following: measles, mumps, rubella, varicella/zoster (chicken pox), yellow fever, rabies, Bacillus Calmette-Guerin (BCG), and typhoid vaccine. Seasonal influenza vaccines for injection are generally killed virus vaccines and are allowed; however, intranasal influenza vaccines (e.g., FluMist®) are live attenuated vaccines and are not allowed. SARS-CoV-2 vaccines are generally mRNA-based or viral vector vaccines (replication-incompetent) and are allowed.

7. Is currently participating in or has participated in a study of an investigational agent or has used an investigational device within 4 weeks prior to the first dose of study intervention.

Note: Participants who have entered the follow-up phase of an investigational study may participate as long as it has been 4 weeks after the last dose of the previous investigational agent.

8. Has a diagnosis of primary immunodeficiency or is receiving chronic systemic steroid therapy (in dosing exceeding 10 mg daily of prednisone equivalent) or any other form of immunosuppressive therapy within 7 days prior to the first dose of study drug.
9. Has an active second malignancy requiring treatment, unless potentially curative treatment has been completed with no evidence of malignancy for 2 years. Participants with the following low-risk or non-invasive malignancies will be allowed:
 - a. Basal cell carcinoma of the skin
 - b. Squamous cell carcinoma of the skin
 - c. Carcinoma in-situ of the cervix
 - d. Carcinoma in-situ of the breast
 - e. Superficial bladder cancer
 - f. Incidental histologic finding of prostate cancer (T1a or T1b using the TNM [tumor, nodes, metastasis] clinical staging system) or prostate cancer that is curative or considered very-low or low risk in which observation is reasonable.
 - g. Other in-situ cancers

Note: The time requirement does not apply to participants who underwent successful definitive resection of basal cell carcinoma of the skin, squamous cell carcinoma of the skin, superficial bladder cancer, in situ cervical cancer, or other in-situ cancers

10. Has known active central nervous system (CNS) metastases and/or carcinomatous meningitis. Participants with previously treated brain metastases may participate provided they are radiologically stable, i.e., without evidence of progression for at least 4 weeks by repeat imaging (note that the repeat imaging should be performed during study screening), clinically stable, and without requirement of steroid treatment for at least 14 days prior to first dose of study intervention.
11. Has severe hypersensitivity (\geq Grade 3) to pembrolizumab and/or any of its excipients.
12. Has active autoimmune disease that has required systemic treatment in the past 2 years (i.e., with use of disease-modifying agents, corticosteroids, or immunosuppressive drugs). Replacement therapy (e.g., thyroxine, insulin, or physiologic corticosteroid replacement therapy for adrenal or pituitary insufficiency, etc.) is not considered a form of systemic treatment and is allowed.
13. Has a history of (non-infectious) pneumonitis that required steroids or has current pneumonitis.

14. Has an active infection requiring systemic therapy. Prophylactic antibiotics/antivirals are allowed.
15. Has a known history of Human Immunodeficiency Virus (HIV) infection.
16. Has known active Hepatitis B virus infection (defined as Hepatitis B [HBV] DNA detected or Hepatitis B surface antigen [HbsAg] positive) or known active Hepatitis C virus infection (defined as Hepatitis C [HCV] RNA qualitative detected). Subjects who have been vaccinated against hepatitis B (positive for hepatitis B surface antibody [HBsAB]) who are negative for other markers of prior hepatitis B infection (e.g., Hepatitis B core antibody [HBcAb] negative) are eligible. Subjects with past exposure or known history of hepatitis B infection (e.g., HBcAb positive) are eligible for the study provided that they are negative by assessment for HBV DNA and HbsAg. Subjects with a history of hepatitis C infection (defined as detectable HCV antibody) are eligible as long as they have a negative HCV viral load.
17. Has a known history of active TB (Bacillus Tuberculosis).
18. Has a history or current evidence of any condition, therapy, or laboratory abnormality that might confound the results of the study, interfere with the subject's participation for the full duration of the study, or is not in the best interest of the subject to participate, in the opinion of the treating investigator.
19. Has known psychiatric or substance abuse disorders that would interfere with cooperation with the requirements of the trial.
20. Is pregnant or breastfeeding or expecting to conceive or father children within the projected duration of the study, starting with the screening visit through 120 days after the last dose of trial treatment.
21. Has had a history of allogenic bone marrow/tissue/solid organ transplant.
22. Has unmeasurable disease by serum/urine testing (oligo-secretory or non-secretory multiple myeloma).
23. Has diagnosis of Waldenstrom's disease, light chain amyloidosis, or POEMS disease.
24. ECOG performance status ≥ 2 .

3.4 Inclusion of Women and Minorities

3.4.1 Eligibility of Women and Minorities

Individuals of any sex/gender, race, or ethnicity are eligible for this study.

3.4.2 Recruitment of Minority Groups

The study recruitment strategy aims to achieve representation of minority groups that reflects the demographics of the affected population in the catchment area.

3.5 Inclusion Across the Lifespan

3.5.1 Age Range of Participants

Individuals ages 18 and over are eligible for this study. Children are excluded from the study because the disease/condition does not occur regularly in children.

3.5.2 Study Design/Recruitment Considerations Related to Age Groups

The study design and recruitment strategy aim to achieve representation of age groups that reflect the demographics of the affected population.

3.6 Duration of Treatment

In the absence of treatment delays due to adverse events (AEs), treatment may continue for up to 2 years or until:

- Disease progression resulting in discontinuation of the study treatment;
- Inter-current illness that prevents further administration of treatment;
- Unacceptable adverse event(s);
- Participant decides to withdraw from the study;
- Significant participant non-compliance with protocol;
- If the participant meets an exclusion criterion (either newly developed or not previously; or, recognized) that precludes further study participation
- General or specific changes in the participant's condition render the participant unacceptable for further treatment in the judgment of the investigator.

3.7 Duration of Follow Up

Participants will be followed for a minimum of 30 days after last treatment or removal from study, or until death, whichever occurs first. Participants removed from study for unacceptable treatment or study-related adverse event(s) will be followed until resolution or stabilization (as determined by the investigator) or until initiation of new anti-cancer therapy, whichever occurs first.

After completing the follow-up period, participants will be followed every 12 weeks (+/- 14 days) to assess for survival/anti-cancer therapy status for up to 1 year after treatment completion or discontinuation. If possible, these visits will be done via video appointment or telephone follow-up.

Long term/Survival Follow-up visits are only required for patients who have either completed 35 cycles of therapy or have discontinued treatment for reasons other than disease progression and have not yet started treatment with another anti-cancer therapy.

Participants who experienced confirmed disease progression or start a new anticancer therapy will be taken off study. Efforts will be made to contact these participants for survival follow-up by telephone every 12 weeks (\pm 14 days) to assess for survival status until death, withdrawal of consent, or the end of the trial, whichever occurs first for up to one year after treatment discontinuation.

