6.1 Study Calendar

Period/ Procedure	Screening	Treatment Cycles (every 3 weeks)							End of Treatment	Safety Follow-up	Long-term Follow-up ¹
Study Day/Visit Day	-28 to -1	C1 D1	C1 D8 (+/- 3)	C2 D1 (+/- 3)	C3 D1 (+/- 3)	C4 D1 (+/- 3)	C5+ D1 (+/- 3) ²		(+/- 21)	30 days (+/- 5) post-EOT	Every 12 weeks (+/- 14) post safety follow-up
Study Treatment/Drug Administration											
Pembrolizumab		X		X	X	X	X				
Administrative Procedures											
Informed consent	X										
Clinical Assessments											
Physical exam ^{3, 4}	X	X	X	X	X	X	X		X		
Medical history	X										
Vital signs ⁴	X	X	X	X	X	X	X		X		
Concomitant medications ⁴	X	X	X	X	X	X	X	X	X	X	
AE assessment	X	X	X	X	X	X	X	X	X	X	
Performance status ⁴	X	X	X	X	X	X	X		X		
Post-treatment anticancer therapy status									X		X
Survival/Long-term Follow-up									X		X

Period/ Procedure	Screening	Treatment Cycles (every 3 weeks)						End of Treatment	Safety Follow-up	Long-term Follow-up ¹
Study Day/Visit Day	-28 to -1	C1 D1	C1 D8 (+/- 3)	C2 D1 (+/- 3)	C3 D1 (+/- 3)	C4 D1 (+/- 3)	C5+ D1 (+/- 3) ²	(+/- 21)	30 days (+/- 5) post-EOT	Every 12 weeks (+/- 14) post safety follow-up
Laboratory Assessments										
Hematology ^{4, 5}	X	X	X	X	X	X	X		X	
Chemistry ^{4, 6}	X	X	X	X	X	X	X		X	
Thyroid Function ^{4, 7}	X	X		X	X	X	X		X	
Tumor marker assessment: Urinalysis ⁸	X						X ¹¹	X ¹¹		X ¹¹
Pregnancy test ^{4, 9}	X	X		X	X	X	X			
Tumor marker assessment: Serum protein and immunofixation electrophoresis (SPEP/SPIE) and serum-free light chains (FLC) ^{4, 10}	X	X					X	X		X
Lymphocyte subsets ⁴		X					X ¹²			
Tissue Collection/ Biopsy										
Bone marrow biopsy ¹¹							X			

¹ Follow-up visits will occur every 12 weeks, up to 1 year after treatment completion or discontinuation. Follow-up visits are only required for patients who have either completed 35 cycles of therapy or have discontinued treatment for reasons other than disease progression and have not yet started treatment with another anti-cancer therapy.

² Up to total of 35 cycles.

³ Full physical exam at screening visit; directed physical exam at all other time points at which a physical exam is indicated

⁴ Assessments to be performed before study treatment administration. Labs can be drawn up to 3 days prior to study treatment administration.

⁵ Including CBC with differential and platelet count

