6.3.4 Safety Follow-Up

Participants will be followed at 30 days (+/- 5 days) after discontinuing study treatment. The following procedures will be performed at Follow Up visit:

- Clinical Assessments
 - Directed physical exam
 - Vital signs
 - Concomitant medications
 - AE assessment
 - Performance status
 - Post-treatment anticancer therapy status
 - The investigator or qualified designee will review all new anti-neoplastic therapy initiated after the last dose of trial treatment. If a participant initiates a new anti-cancer therapy within 30 days after the last dose of trial treatment, the 30-day Safety Follow-up visit must occur before the first dose of the new therapy. Once new anti-cancer therapy has been initiated the participant may be taken off study.
 - Survival/long-term follow-up
- Laboratory Assessments
 - Hematology
 - Chemistry
 - Thyroid function

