6.3.5 Long Term/Survival Follow-up

After completing the follow-up period, participants will be followed every 12 weeks (+/- 14 days) to assess for survival/anti-cancer therapy status for up to 1 year after treatment completion or discontinuation. If possible, these visits will be done via video appointment.

Long term/Survival Follow-up visits are only required for patients who have either completed 35 cycles of therapy or have discontinued treatment for reasons other than disease progression and have not yet started treatment with another anti-cancer therapy.

The following procedures will be performed at each Long-Term/Survival Follow-Up visit:

- Clinical Assessments
 - Concomitant medications
 - AE assessment
 - Post-treatment anticancer therapy status
 - Survival/long-term follow-up
- Laboratory Assessments (review of markers if indicated)
 - Tumor marker assessment: urinalysis – 24-hour UPEP/UPIE (if clinically indicated)

- Tumor marker assessment: Serum protein and immunofixation electrophoresis (SPEP/SPIE) and serum FLC (free light chains)

Participants who experienced confirmed disease progression or start a new anticancer therapy will be taken off study. Efforts will be made to contact these participants for survival follow-up by telephone every 12 weeks (\pm 14 days) to assess for survival status until death, withdrawal of consent, or the end of the trial, whichever occurs first for up to one year after treatment discontinuation.

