6.4.2 Acceptable Concomitant Medications

All treatments that the investigator considers necessary for a participant's welfare may be administered at the discretion of the investigator in keeping with the community standards of medical care. This includes supportive care measures such as antimicrobial/antiviral prophylaxis and intravenous immunoglobulin therapy for hypogammaglobulinemia. All concomitant medication will be recorded on the case report form (CRF) including all prescriptions, over the counter (OTC), herbal supplements, and IV medications and fluids. If changes occur during the trial period, documentation of drug dosage, frequency, route, and date may also be included on the CRF.

All concomitant medications received within 28 days prior to the first dose of trial intervention and up to 30 days after the last dose of trial intervention should be recorded. Concomitant medications administered after 30 days after the last dose of trial intervention should be recorded for SAEs and events of clinical interest (ECIs) as defined in Section 8.3.

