9.3.2 Secondary Analysis (or Analysis of Secondary Endpoints)

Continuous data will be summarized using descriptive statistics such as means, medians, standard deviations, and ranges. Categorical data will be summarized using frequency counts and percentages. Graphical summaries of selected endpoints may also be presented.

Secondary Objective and Endpoints #1 - Safety and Tolerability Analysis: The safety population will consist of all participants who receive any amount of study treatment. Safety will be assessed by evaluation of AEs. The safety analyses will be performed using the safety population. Specific AEs will be counted once for each participant for calculating rates but will be presented in total in participant listings.

Secondary Objective and Endpoints #2 -Depth of Response

Point estimate and exact binomial confidence interval will be reported for the proportion of patients achieving PD (progressive disease), SD (stable disease), PR (partial response), VGPR (very good partial response), CR (complete response), and sCR (stringent complete response) for best-achieved response at any time during pembrolizumab therapy.

Secondary Objective and Endpoints #3 -Time to Event Outcomes

For overall survival (OS), participants who remain alive at the end of study follow-up will be censored at the time when they are known to be alive. For progression-free survival (PFS), participants without progression or death will be censored at the time of the last evaluable disease assessment, while participants without a disease assessment will be censored at the date of first study treatment received. OS and PFS will be summarized using the Kaplan-Meier (KM) method. The 12-months event-free probabilities, 25th percentile, median, and 75th percentile, along with their corresponding 95% confidence intervals, will be reported. Median duration of response among the responders will be reported along with 95% confidence intervals. Competing risks analysis will be performed for analyzing time to next treatment (TNT), with death as a competing event. For patients who are alive and do not receive the next line of therapy, TNT will be censored at the last study contact. Cumulative incidence function, along with 95% confidence intervals, will be reported for TNT.

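### After progression, nothing requires the start of next therapy to be recorded beyond the 30-day safety visit, although that start is the time-to-next-treatment event.

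*Combined protocol and SAP*

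**What the plan says.** Section 7.1.3 measures TNT from the start of study treatment to the start of the next line of therapy. Section 2.3 lists it as a secondary endpoint running to the end of follow-up.

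Next-therapy status is collected at two kinds of contact:

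- **Safety visit, 30 days (±5) after treatment (6.1, 6.3.4).** "The investigator or qualified designee will review all new anti-neoplastic therapy initiated after the last dose of trial treatment".
- **12-weekly long-term visits (6.1, 6.3.5).** These carry the calendar row for anticancer therapy after treatment. Footnote 1 of the calendar limits them: "Follow-up visits are only required for patients who have either completed 35 cycles of therapy or have discontinued treatment for reasons other than" progression, and who have not begun another therapy. Sections 3.7 and 6.3.5 repeat the limit.

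For progressors, 3.7 states: "Participants who experienced confirmed disease progression or start a new anticancer therapy will be taken off study". What follows is "Efforts will be made to contact these participants for survival follow-up by telephone every 12 weeks", for up to one year, and survival is the only status those calls are to establish. Concomitant medication recording does not fill the gap: "Concomitant medications administered after 30 days after the last dose of trial intervention should be recorded for SAEs and events of clinical interest" (6.4.2).

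On analysis, 2.3 has "TNT, PFS, OS assessed using Kaplan-Meier survival analysis", and 1.4 also names Kaplan-Meier for the time-to-event outcomes. Section 9.3.2 has "Competing risks analysis will be performed for analyzing time to next treatment (TNT), with death as a competing event", and "For patients who are alive and do not receive the next line of therapy, TNT will be censored at the last study contact".

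**The concern.** Progression is the usual reason for starting another therapy. The plan therefore stops requiring the TNT event to be collected in the participants most likely to have it, within about a month of their stopping treatment.

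The censoring rule does not repair this, because the last contact is not defined:

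- **If a survival call counts,** a participant treated after the safety visit stays in the risk set as untreated. A later death is then counted as death before next therapy. TNT incidence is too low.
- **If the safety visit is the last contact,** progressors are censored just as their chance of starting therapy is high. The censoring is informative, and the direction of the error depends on how quickly therapy starts.

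Section 1.4 allows comparison of the time-to-event results with historical controls. A falsely low TNT incidence would look favourable there.

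**Working it through.** **Where a progressor's next therapy is recorded**

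| Contact | Required for progressors? | Next therapy recorded? |
|---|---|---|
| Safety visit, 30 (±5) days (6.1, 6.3.4) | Yes | Yes |
| 12-weekly long-term visit (3.7, 6.1, 6.3.5) | No | Yes |
| 12-weekly telephone call (3.7, 6.3.5) | Best effort | Not listed; survival only |
| Concomitant medication record after day 30 (6.4.2) | Only for SAEs and events of clinical interest | Not in general |

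The last contact that is both required and asks about therapy is the safety visit. This result rests on the text alone. The plan states no TNT figure to reproduce.

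**Share of starts falling after day 30.** Assume an exponential gap with median *m* days from the end of treatment. The share is 2^(−30/*m*): 23% for *m* = 14, 48% for *m* = 28 and 69% for *m* = 56.

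**Illustration of the effect at 12 months.** None of these inputs is in the documents:

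- 80% of participants progress: 80% of them at day 84 (0.64 of the cohort) and 20% at day 168 (0.16).
- 70% of progressors take further therapy, with a median gap of 30 days: λ = ln 2/30 = 0.02310 per day.
- Median survival after progression is 8 months (243.5 days): μ = ln 2/243.5 = 0.00285 per day.
- Non-progressors have no events. Every start by day 30 is captured and none later.

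Start before death, per progressor:

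- Factor λ/(λ+μ) = 0.890.
- Eventually: 0.7 × 0.890 = 0.623.
- By day 30: 0.623 × (1 − e^(−0.02595×30)) = 0.623 × 0.541 = 0.337.
- Death without a start by day 30: 0.7 × 0.110 × 0.541 + 0.3 × (1 − e^(−0.00285×30)) = 0.066.

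12-month incidence with death competing:

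1. *True:* 0.80 × 0.623 ≈ 0.50. Nearly all starts fall inside 12 months.
2. *Survival call as last contact:* 0.80 × 0.337 = 0.27.
3. *Censored at the safety visit:* the first group contributes 0.64 × 0.337 = 0.216 starts and 0.64 × 0.066 = 0.042 deaths, leaving event-free probability 0.742. The rest of that group is censored, so 0.36 of the cohort remains at risk. The second group adds 0.742 × (0.16 × 0.337)/0.36 = 0.111. Total 0.33.

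Simulation with 300,000 participants gives 0.496, 0.268 and 0.325. The Kaplan-Meier version, with deaths censored, gives 0.54, 0.28 and 0.34. In 25 participants this is about 12 true events against 7 or 8. The 95% half-width on 0.50 is 1.96 × √(0.25/25) = 0.20.

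**Sensitivity (competing-risks estimate).** The grid has 80 scenarios: 60–100% progressing, 30–100% uptake, median gap 7–60 days.

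| Reading | Median gap | Estimate minus truth |
|---|---|---|
| Survival call | 7–60 days | −0.50 to −0.01; negative in all 80 |
| Safety visit | 30–60 days | −0.37 to −0.03 |
| Safety visit | 14 days | −0.11 to +0.07 |
| Safety visit | 7 days | −0.02 to +0.16 |

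The −0.50 needs 100% progressing, 100% uptake and a 60-day gap. At 14 days the error is positive only with at least 90% progressing and at most 70% uptake.

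In the illustration, varying median survival after progression from 4 to 24 months gives 0.45–0.54 true, 0.26–0.28 (call) and 0.31–0.34 (visit).

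**The case against.** **The text may be ambiguous rather than silent.** Sections 3.7 and 6.3.5 open with a general sentence that follows participants every 12 weeks for both survival and anticancer therapy. A reader could carry the second item into the calls. But the next paragraph in each section limits the required visits to a group that excludes progressors. A separate paragraph then gives progressors their own contact and names survival alone. On the most generous reading the sections disagree, and the same edit is needed.

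**Starts may be found anyway.** This is a single-centre study with medical records as source (3.1, 10.6), and 9.3.2 censors only those who have not received further therapy, which presupposes that status is known. Both points are fair. Capture will probably exceed the zero after day 30 assumed above, but nothing in the plan requires the search.

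**The size depends on choices.** This stands.

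- The calendar dates the safety visit from an end-of-treatment visit with its own ±21-day window. A visit at day 56 (30 + 5 + 21) narrows the illustration to 0.38 (call) or 0.44 (visit) against 0.50. A visit at day 9 (30 − 21) widens it to 0.10 or 0.14.
- Section 6.3.4 puts the safety visit before the first dose of any new therapy begun within 30 days of the last study dose. Even early starts might then be recorded only as planned, so full capture to day 30 may be generous.
- Eligibility (3.3.1, criterion 6) excludes candidates for regimens of known benefit, so uptake may be below 70%. With 30% uptake and a 14-day gap the figures are 0.23 true against 0.18 (call) or 0.22 (visit).

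**The endpoint is minor.** TNT is descriptive, in about 25 participants, and no decision uses it. This limits the importance of the gap but does not remove it.

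**Conclusion.** The point holds. For participants who progress, the plan requires no record of the next-therapy start after the 30-day safety visit, and it censors TNT at a contact it does not define. That conclusion rests on the text and needs no assumption.

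The size is conditional on the assumed rates and on no later start being found by other means. Treating survival calls as last contact biases incidence low in every scenario examined. Censoring at the safety visit biases it low at median gaps of 30–60 days, but the error can be small or positive at about 14 days or less. In the main illustration the shortfall is 0.17 to 0.23 on a true value of 0.50, similar to the sampling half-width of 0.20. Unlike sampling error, it would not shrink with more participants.

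The Kaplan-Meier and competing-risks statements conflict whatever is assumed about follow-up. The effect is confined to one secondary endpoint. The change should be made, because an unrecorded start date may be hard to recover later.

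**What to change.** 1. In 3.7 and 6.3.5, have the 12-weekly call to progressors, or a chart review, record the start date of the next anticancer therapy as well as survival.
2. In the 6.1 calendar, extend the row for anticancer therapy after treatment to everyone in follow-up, and amend footnote 1 to match.
3. In 9.3.2, censor TNT at the last date on which next-therapy status was known.
4. Reconcile the TNT method in 1.4 and 2.3 with 9.3.2.
5. Reconcile the wording on leaving the study and continued monitoring after progression across 3.7, 6.3.3, 6.3.5, 6.6 and 6.7. Section 6.3.3 makes leaving the study optional where 3.7 and 6.3.5 make it definite.

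The cost is one question on a call already planned (or chart review at a single centre), one CRF field and text edits. No visits are added.
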